Appendix 1: Quality assurance checklists

Checklist for oropharyngeal swab (OPS) including palatine tonsils						
Name:		Correct	Incorrect	Not relevant		
1	OPS performed with proper use of protection equipment					
2	OPS performed in compliance with infection prevention guidelines					
3	OPS performed in alignment with the participant ensuring proper visualization of the back wall of the oropharynx					
4	The swab is placed correctly between thumb, index and middle finger					
5	Participant is instructed to say “aaaah” making the soft palate rises and a spatula is used					
6	The swab is inserted and retracted without making contact with the mucous membrane of the oral cavity or the tongue					
7	The swab gathers sufficient material from the back wall of the oropharynx including both palatine tonsils in a rotating or brushing movement					
8	The swab is placed in the sample tube in accordance with local guidelines					
Total score						
		Poor	Unacceptable	Good	Acceptable	Excellent
General assessment						

Checklist for oropharyngeal swab (OPS) excluding palatine tonsils

Name:		Correct	Incorrect	Not relevant		
1	OPS performed with proper use of protection equipment					
2	OPS performed in compliance with infection prevention guidelines					
3	OPS performed in alignment with the participant ensuring proper visualization of the back wall of the oropharynx					
4	The swab is placed correctly between thumb, index and middle finger					
5	Participant is instructed to say “aaaah” making the soft palate rises and a spatula is used					
6	The swab is inserted and retracted without making contact with the mucous membrane of the oral cavity or the tongue					
7	The swab gathers sufficient material from the back wall of the oropharynx in a rotating or brushing movement					
8	The swab is placed in the sample tube in accordance with local guidelines					
Total score						
		Poor	Unacceptable	Good	Acceptable	Excellent
General assessment						

Appendix 2: Survey for participants

Survey to be filled out by participant

1. Are you vaccinated against COVID-19?

YES

NO

2. Have you previously been infected with COVID-19?

YES

NO

3. Please indicate your reason for getting tested today:

Symptoms

Close contact

Positive quick test

Screening

Test ahead of social gathering or nursing home visit

Other

If 'yes' to symptoms, which symptoms do you have?

Sore throat

Headache

Cough

Muscle and joint pain

Fever

Fatigue

Reduced sense of smell or taste

If "yes" to symptoms, for how many days have you had symptoms?

Indicate number of days: _____ day(s)

4. Have you had your tonsils removed??

YES

NO

5. On a scale from 0-10, how uncomfortable was today's test for COVID-19?

No discomfort

Worst possible discomfort

To be filled out by personnel:

REDCap ID: _____

Personnel ID: _____

Participant's Mallampati score:

1

2

3

4

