After enrollment, the participants will be randomized in a 1:1 ratio having either oropharyngeal swab performed including the posterior oropharyngeal wall and both palatine tonsils (intervention group) or only including the posterior oropharyngeal wall and avoiding the palatine tonsils (control group), see Figure B.

A block randomization list was generated by [name] using an online randomization software⁽⁷⁾ afterward uploaded to REDCap. The randomization group will be disclosed in connection with trial registration in REDCap using the REDCap “randomize” function. The oropharyngeal sample will afterward be performed by the trained healthcare workers with or without the palatine tonsils depending on the randomization to either the intervention or control group.

Figure B. Study flowchart.

The swabs will be placed in separate tubes dry and sent to the clinical microbiology laboratory for detection of SARS-CoV-2 by single-target RT-PCR at Statens Serum Institute. Samples with viral cycle threshold (Ct) values below 38 are considered positive, 38-40 inconclusive and above 40 negative⁽⁸⁾.

All participants are required to fill out a survey on-site about their reason for being tested, prior Covid-19 infection(s), vaccinations status, symptoms, and if any prior tonsillectomy has been performed (appendix 2).

All healthcare workers participating in the data collection have been given a unique ID which will be registered for each OPS performed in the study. Further, the healthcare worker will also be asked to rate the Mallampati score of the participants including in the study (appendix 5).

All data will be documented on-site in a secure web database (REDCap, appendix 3).

Outcomes

The primary outcome will be reported as:

- SARS-CoV-2 RNA by RT-PCR test result (positive, negative, inconclusive)

The secondary outcome will be reported as:

- SARS-CoV-2 RT-PCR cycle threshold (Ct) value
- Test discomfort on a 11-point NRS-scale
- Development of COVID-19 disease after testing
- SARS-CoV-2 detection rate for each healthcare worker
- Mallampati Score of participants being tested

Sample size

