Appendix 3: REDCap database

REDCap-ID	
Date	DD-MM-YYYY
Randomization	Oropharyngeal swab including palatine tonsils Oropharyngeal swab excluding palatine tonsils
CPR-number	
Sample ID	
Are you vaccinated against COVID-19?	YES NO
Have you previously been infected with COVID-19?	YES NO
Please indicate your reason your reason for getting tested today	Symptoms Close contact Positive quick test Screening Test ahead of social gathering / visit to a nursing home Other
If "YES" to symptoms, what symptoms do you have?	Sore throat Headache Cough Muscle and joint pain Fever Fatigue Reduced sense of smell or taste
If "YES" to symptoms, for how many days have you had symptoms?	
Have you had your tonsils removed?	YES NO
On a scale from 0-10, how uncomfortable was today's test for COVID-19?	0 1

	2 3 4 5 6 7 8 9 10
Personnel ID	
Participant's Mallampati score	1 2 3 4
FOLLOW UP	
Have you since the test and until four weeks later had symptoms of COVID-19?	YES NO
If 'yes' to symptoms, when did you develop symptoms?	I had symptoms when I got tested I developed symptoms 1-3 days after the test I developed symptoms 3-5 days after the test I developed symptoms 5-7 days after the test I developed symptoms 1-2 weeks after the test I developed symptoms 2-3 weeks after the test I developed symptoms 3-4 weeks after the test I do not know / I do not wish to disclose
If 'yes' to symptoms, which symptoms did you develop?	Sore throat Headache Cough Muscle- / joint pain Fever Fatigue Reduced sense of smell / taste Other
If 'yes' to fever, what was your highest temperature?	

If 'yes' to fever, how many days did you have a fever for?	
If 'yes' to symptoms, how many days did you have symptoms in total?	
Think about period from one week before your test until four weeks after. Which of the following statements describes best how you felt at your worst?	
I had no symptoms
 
I was sick and stayed home
 
I was admitted to the hospital due to COVID-19

Have you taken days off work / from school during your infection with COVID-19?	
No, I have not taken any days off
 
Yes, I have taken days off between one week before the test until four weeks after
 
Yes, I have taken days off later than four weeks after
 
Not relevant

If 'yes' to having taken days off, how many days have you taken off in total?	
Do you smoke?	
Yes
 
No
 
I used to smoke, but I do not smoke anymore
 
Not relevant / I do not wish to disclose

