We planned to do a sensitivity analysis using a lower cycle threshold (Ct) < 25 for positive SARS-CoV-2 definition to explore the consequences of a higher test specificity for the SARS-CoV-2 detection rate between specimen types. We also plan to estimate the sensitivity and specificity using Bayesian latent class analysis for accounting for an imperfect reference standard. Further, we planned to do subgroup analyses exploring the distribution of positive test results for participants stratified by symptoms, previous COVID-19 infection, vaccinations status, prior tonsillectomy and Mallampati score. To explore a potential bias from the distribution of the inconclusive test results, we excluded the inconclusive results in a subgroup analyses.

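### At baseline, current symptoms are recorded only through the reason-for-testing item, so ill participants who give another reason may be counted as symptom-free in the planned symptom subgroup

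*Combined protocol and SAP*

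**What the plan says.** The protocol enrols people with and without symptoms (Eligibility criteria). Under Randomization it describes a survey "about their reason for being tested, prior Covid-19 infection(s), vaccinations status, symptoms" and prior tonsillectomy, so reason and symptoms are listed as separate content. SAP 2.5 likewise lists test reason and symptom description as separate baseline characteristics. Both the protocol and SAP 3.1 plan to explore positive results for "participants stratified by symptoms, previous COVID-19 infection, vaccinations status, prior tonsillectomy and Mallampati score".

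The forms are narrower. Item 3 of Appendix 2 reads "Please indicate your reason for getting tested today" and offers *Symptoms*, *Close contact*, *Positive quick test*, *Screening*, a social gathering or nursing home visit, and *Other*. Two conditional questions follow: "If 'yes' to symptoms, which symptoms do you have" and "If 'yes' to symptoms, for how many days have you had symptoms". In Appendix 3 the reason field is followed by "If 'YES' to symptoms, what symptoms do you have", with no baseline yes/no field for symptoms.

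The follow-up part of Appendix 3 asks when symptoms began. One answer is "I had symptoms when I got tested". The protocol's Follow-up section describes this contact only for participants who test positive and agree, about one month later.

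**The concern.** The forms record why a person came, whereas the subgroup needs to know whether the person was ill. The two come apart for someone with a sore throat who comes because a home test was positive or a household member is ill. That person can answer item 3 truthfully without ticking *Symptoms*.

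The plan does not say how the symptom strata are formed. A blank symptom field could mean no symptoms, a question skipped because of the reason given, or a missing answer. SAP 3.3 keeps participants with missing questionnaire data in the primary and secondary analyses and leaves them out of the baseline table, but gives no rule for the subgroup. If blanks are read as no symptoms, that stratum mixes screened people with ill people. Test-negatives are not followed up, so their status cannot be recovered later.

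**Working it through.** **The plan's own figure.** With 20% v 25% positive, two-sided 5% and 80% power, without continuity correction, n per arm = [1.96 × √(2 × 0.225 × 0.775) + 0.8416 × √(0.20 × 0.80 + 0.25 × 0.75)]² / 0.05² = 1,094, or 2,188 in total. This matches the Sample size section. The point does not depend on it; 2,188 serves only as a base for counts.

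**How many could be misclassified.** Let s be the share truly symptomatic and m the fraction of these who tick only another reason. Neither is in the documents, so both are assumed. If blanks are coded as no symptoms, the symptomatic share of the labelled no-symptom group is c = s·m / (1 − s + s·m), and the count is 2,188·s·m.

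| s | m = 5% | m = 30% |
|---|---|---|
| 40% | 0.02/0.62 = 3% (44 people) | 0.12/0.72 = 17% (263) |
| 60% | 0.03/0.43 = 7% (66) | 0.18/0.58 = 31% (394) |
| 80% | 0.04/0.24 = 17% (88) | 0.24/0.44 = 55% (525) |

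**Effect on positivity.** Assume control-arm positivity of 35% with symptoms and 5% without. The labelled no-symptom group then reads 5(1 − c) + 35c, which is 8%, 11% or 14% at c = 10%, 20% or 30%, instead of 5%.

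**Effect on relative detection.** Two cases:
- The effect differs, with ratio 1.25 in ill people and 1.00 in others (assumed). The intervention arm reads 5(1 − c) + 43.75c = 8.875%, 12.75% or 16.625%. The ratio in the labelled no-symptom group becomes 1.11, 1.16 or 1.19 instead of 1.00.
- The effect is the same, 1.25 in both strata. The intervention arm reads 6.25(1 − c) + 43.75c, which is 1.25 times the control figure at every c. The ratio is not biased.

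**What is not touched.** Under SAP 3.1 the primary model contains group, test center and clustering by healthcare worker; symptoms do not enter. The discomfort item is on the same sheet and SAP 2.5 has it answered immediately after testing, so the sheet appears to be completed before the result is known. Misclassification should therefore not depend on the PCR result itself.

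**The case against.** The strongest reply is that a reader might infer more than the forms show.

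- *Ill people tested for another reason necessarily land in the no-symptom group.* The documents do not support this. Neither form limits item 3 to one answer, the survey is on paper so the symptom list is in front of everyone, and an ill contact may tick two reasons. No no-symptom stratum is defined, and nothing says blanks count as no symptoms. Misclassification is likely, not certain. What remains is that the item still asks for a reason, and the missing instruction is itself a gap.
- *The outcome of COVID-19 disease after testing loses its baseline.* It does not. The follow-up answer on symptoms present at the test separates existing from new illness among those followed up. It is recalled after about a month and reaches only consenting positives, so it cannot rebuild the subgroup, whose denominators include test-negatives.
- *An unlisted symptom cannot be recorded.* It can: the participant may tick *Symptoms* and give the number of days. Only its type is lost, because the baseline list lacks the *Other* option found at follow-up.
- *The subgroup effect will be biased.* Only if the effect differs by symptoms, and the sample size assumes a single 25% improvement. Even in the case worked with a true difference, the shifts are small beside sampling error. With half of 2,188 symptomatic (0.5 × 35% + 0.5 × 5% = 20%), the labelled group holds 1,094/(1 − c) people, and unadjusted 95% intervals for 1.11, 1.16 and 1.19 are 0.77–1.61, 0.87–1.55 and 0.94–1.50.

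It is also fair that the subgroup is exploratory. These replies limit the consequences; they do not supply the missing question.

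**Conclusion.** The point holds in a limited form. Baseline symptom status rests on a reason-for-testing answer, while the plan treats symptoms as a separate variable and stratifies by it. The damage is confined to the symptom subgroup and the baseline symptom description. Positivity in the no-symptom stratum would be overstated; masking of a difference in effect requires that such a difference exists. Every size given rests on assumed values of s, m and positivity, and on blanks being read as no symptoms. The range is wide enough (3% to 55% contamination) that the problem could be trivial or serious for that subgroup. It is worth correcting because status is lost for test-negatives once the visit is over.

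**What to change.** In Appendices 2 and 3, add a separate question for everyone ahead of the reason for testing: *Do you have symptoms today? YES/NO*. Make the symptom list and number of days depend on that answer, and state whether the reason item takes one answer or several. In SAP 3.1, define the symptom subgroup by the new item, with blanks treated as missing and not as no symptoms. Adding *Other* to the baseline symptom list, to match follow-up, is optional.

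The cost is one tick-box, one database field and a sentence in the SAP, with no extra visit or staff. If the forms are already in use, keep the data as collected, label the stratum *tested because of symptoms*, and state how blanks were handled.

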Appendix 3: REDCap database

REDCap-ID	
Date	DD-MM-YYYY
Randomization	Oropharyngeal swab including palatine tonsils Oropharyngeal swab excluding palatine tonsils
CPR-number	
Sample ID	
Are you vaccinated against COVID-19?	YES NO
Have you previously been infected with COVID-19?	YES NO
Please indicate your reason your reason for getting tested today	Symptoms Close contact Positive quick test Screening Test ahead of social gathering / visit to a nursing home Other
If "YES" to symptoms, what symptoms do you have?	Sore throat Headache Cough Muscle and joint pain Fever Fatigue Reduced sense of smell or taste
If "YES" to symptoms, for how many days have you had symptoms?	
Have you had your tonsils removed?	YES NO
On a scale from 0-10, how uncomfortable was today's test for COVID-19?	0 1

	2 3 4 5 6 7 8 9 10
Personnel ID	
Participant's Mallampati score	1 2 3 4
FOLLOW UP	
Have you since the test and until four weeks later had symptoms of COVID-19?	YES NO
If 'yes' to symptoms, when did you develop symptoms?	I had symptoms when I got tested I developed symptoms 1-3 days after the test I developed symptoms 3-5 days after the test I developed symptoms 5-7 days after the test I developed symptoms 1-2 weeks after the test I developed symptoms 2-3 weeks after the test I developed symptoms 3-4 weeks after the test I do not know / I do not wish to disclose
If 'yes' to symptoms, which symptoms did you develop?	Sore throat Headache Cough Muscle- / joint pain Fever Fatigue Reduced sense of smell / taste Other
If 'yes' to fever, what was your highest temperature?	

If 'yes' to fever, how many days did you have a fever for?	
If 'yes' to symptoms, how many days did you have symptoms in total?	
Think about period from one week before your test until four weeks after. Which of the following statements describes best how you felt at your worst?	
I had no symptoms
 
I was sick and stayed home
 
I was admitted to the hospital due to COVID-19

Have you taken days off work / from school during your infection with COVID-19?	
No, I have not taken any days off
 
Yes, I have taken days off between one week before the test until four weeks after
 
Yes, I have taken days off later than four weeks after
 
Not relevant

If 'yes' to having taken days off, how many days have you taken off in total?	
Do you smoke?	
Yes
 
No
 
I used to smoke, but I do not smoke anymore
 
Not relevant / I do not wish to disclose

If 'yes' to smoking, which of the following statements describes you best?	
I smoke sometimes, e.g. at parties
 
I smoke daily (less than 10 cigarettes or equivalent to that)
 
I smoke daily (10 or more cigarettes or equivalent to that)
 
I smoke e-cigarettes
 
I do not know / I do not wish to disclose

If 'yes' to having smoked previously, which statement describes you best?	
I have not smoked for more than 5 years
 
I have smoked within the last 5 years, but I do not smoke anymore

Think about the past half year before the test. Which of the following statements describes your level of physical activity best?	
I do hard exercise / elite level sports regularly and several times per week
 
I exercise or perform heavy gardening tasks or similar at least four times per week
 
I walk, bike or do other lighter exercise at least four times per week (incl. walking/biking to work and lighter gardening)
 
I read, watch TV or do other still activities
 
I do not know / I do not wish to disclose

Think about the past half year before the test. How would you describe you physical condition?
	
Very good Good Alright Below average Bad I do not know / I do not wish to disclose

Have you been diagnosed with a chronic illness by a doctor previous to your test for COVID-19?
	
No, I have not been diagnosed with a chronic illness Yes, diabetes Yes, asthma Yes, COPD or chronic pulmonary disease Yes, high blood pressure Yes, chronic of frequent headache, including migraine Other chronic illnesses I do not know / I do not wish to disclose

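### The follow-up severity item has no true answer for symptoms without staying home, and the onset brackets share end points and omit onset later on the test day

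*Combined protocol and SAP*

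**What the plan says.** The protocol (Follow-up) sends a questionnaire or makes a phone call about one month after a positive result, to participants who agreed to be contacted, and refers to Appendix 3 for the questions.

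The severity item there covers one week before the test to four weeks after it. It asks "Which of the following statements describes best how you felt at your worst" and offers three answers: "I had no symptoms", "I was sick and stayed home" and "I was admitted to the hospital due to COVID-19". The next item, on absence from work or school, includes the answer "No, I have not taken any days off".

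The onset item has one answer for symptoms already present at the test and then a run of brackets: "I developed symptoms 1-3 days after the test I developed symptoms 3-5 days after the test I developed symptoms 5-7 days after the test", followed by 1-2, 2-3 and 3-4 weeks, and a do-not-know answer.

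The development of COVID-19 disease after the test is a secondary outcome in the protocol (Outcomes) and in the SAP (Outcome definitions). Neither document says which items define it, how it is graded, or what model applies to it.

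**The concern.** A response list should give every respondent one true answer. The severity list does not: between no symptoms and staying home there is no place for a person with, say, a sore throat who carried on as usual. The form itself expects such people, because the absence item lets an infected person report no days off. The onset list gives two valid answers on some days and none on the test day.

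What is at stake is how severity and timing are described among the test-positive participants who are followed up. The same-day gap matters a little more than the overlaps. The outcome's name turns on whether disease came after the test, and a person whose symptoms began hours after the swab may pick the answer for symptoms already present.

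**Working it through.** The documents give no figure on this point to reproduce, so the check is a reading of the response options and a count of days.

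**Severity item.** Take a participant with symptoms who did not stay home and was not admitted.

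| Answer offered | True for this person? |
|---|---|
| No symptoms | No |
| Sick and stayed home | No, the second half is false |
| Admitted to hospital | No |

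None of the 3 answers fits.

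**How much the other items recover.** Appendix 3 also asks for any symptoms since the test (yes/no), which symptoms, highest temperature, days of fever, total days of symptoms, and days off.

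- If the person chose no symptoms but answered yes to the symptom item, the contradiction is visible and the person can be recoded as symptomatic.
- If the person chose stayed home but reported no days off, the answer is doubtful but not disproved. Staying home on days without work or school needs no day off.
- If the person chose stayed home and marked the days-off item as not relevant, the form cannot separate a true answer from a forced one.
- The windows differ. The severity item starts one week before the test and the symptom item starts at the test. A mild illness that ended before the test leaves no contradiction to find.

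Recovery is therefore real but partial, and no reconciliation rule is given.

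**Onset item.** Map each whole day after the test to the printed brackets, counting both end points: 1-3, 3-5, 5-7, 7-14, 14-21 and 21-28 days.

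| Day of onset | Brackets that fit |
|---|---|
| 0 (later on the test day) | none |
| 3 | 1-3 and 3-5 days |
| 5 | 3-5 and 5-7 days |
| 7 | 5-7 days and 1-2 weeks |
| 14 | 1-2 and 2-3 weeks |
| 21 | 2-3 and 3-4 weeks |
| all other days from 1 to 28 | exactly one |

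Five of 28 days are ambiguous and 28 − 5 = 23 are not. On each ambiguous day the two candidates are neighbours, so the error is one bracket at most. A shared end point cannot move a person between onset before and onset after the test. Only the gap at day 0 can do that, because the choices left are present at testing, 1-3 days, or do not know. The on-site survey (Appendix 2) records symptoms as a reason for testing and could help to detect this, but no rule says that it will be used.

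**Check of the replacement brackets.** Later the same day to day 2, then days 3-4, 5-7, 8-14, 15-21 and 22-28 hold 3 + 2 + 3 + 7 + 7 + 7 = 29 days. That covers day 0 to day 28 once each.

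**The case against.** The strongest reply is that little is lost. Whether symptoms occurred is answered by the yes/no item, and the answer for symptoms already present separates earlier from later onset. Fever, duration and absence carry severity information of their own. The stem asks for the best-fitting statement, so a coarse scale may be intended. Onset is recalled about a month later, and ambiguity at a bracket limit probably adds little to recall error. No analysis model in the SAP uses either item.

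Most of this stands, and it keeps the point small. It does not remove it. Staying home is a fact rather than a degree, so a best-fit reading does not make the middle answer true. Days off is only a proxy for staying home. The same-day gap touches the before-or-after distinction itself.

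Stronger readings are tempting, and the documents do not support them:

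- A reader might infer that these two items are the only source for severity and timing, or that the data are beyond repair. The neighbouring items contradict both.
- A reader might multiply the roughly 438 expected positives by some share with mild illness to count those affected. The documents give no such share, and only positives who agree to contact are followed up.
- A reader might infer bias between the arms. Both arms receive the same form, and nothing in the documents points to differential error.

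**Conclusion.** The point holds as a minor flaw in form design. The severity item records a participant with symptoms who did not stay home wrongly, whichever answer is chosen. The onset item is non-unique on five of days 1 to 28, by one adjacent bracket, and has no place for onset later on the test day. The effect is limited to the descriptive severity and timing of one secondary outcome, with partial recovery from other items. The primary outcome, Ct value and discomfort score do not use these items.

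This rests on three assumptions: the form is used as printed, respondents choose one of the substantive answers, and days are counted as whole days with both bracket limits included. The number of participants affected cannot be derived from the documents.

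**What to change.** Before follow-up starts, make two edits in REDCap:

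1. In the severity item, add *I had symptoms but did not stay home* between the first and second answers.
2. In the onset item, replace the brackets with later the same day to day 2, days 3-4, 5-7, 8-14, 15-21 and 22-28. Keep the existing answer for symptoms present at the test and the do-not-know answer.

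It would help to add one sentence to the SAP (Outcome definitions) naming the items that define the outcome on disease after the test, since the form edits alone leave that open.

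The cost is an edit to two items and one sentence of text. It needs no extra contacts, staff or participants.
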